11.0 STUDY MANAGEMENT

11.1 Institutional Review Board (IRB) Approval and Consent

It is expected that the IRB will have the proper representation and function in accordance with federally mandated regulations. The IRB should approve the consent form and protocol.

In obtaining and documenting informed consent, the investigator should comply with the applicable regulatory requirement(s), and should adhere to Good Clinical Practice (GCP) and to ethical principles that have their origin in the Declaration of Helsinki.

Before recruitment and enrollment onto this study, the patient will be given a full explanation of the study and will be given the opportunity to review the consent form. Each consent form must include all the relevant elements currently required by the FDA Regulations and local or state regulations. Once this essential information has been provided to the patient and the investigator is assured that the patient understands the implications of participating in the study, the patient will be asked to give consent to participate in the study by signing an IRB approved consent form.

Prior to a patient's participation in the trial, the written informed consent form should be signed and personally dated by the patient and by the person who conducted the informed consent discussion.

11.2 Amendments

The Principal Investigator will formally initiate all amendments to the protocol and/or informed consent. All amendments will be subject to the review and approval of the appropriate local, institutional, and governmental regulatory bodies, as well as by BMS and Abbvie. In the event that external participating sites are added, amendments will be distributed by the lead institution (Northwestern) to all external sites upon approval by the Northwestern University IRB.

11.3 Registration Procedures

Patients may not begin protocol treatment prior to registration. All patient registrations will be registered centrally through the Clinical Research Office at Northwestern University before enrollment to study. Please contact the assigned QAM or email the QA Department ([contact]) for questions regarding patient registration.

Prior to registration, eligibility criteria must be confirmed by the assigned QAM. The study coordinator will screen all subjects for potential registration via the web-based application NOTIS (Northwestern Oncology Trial Information System), which is available at: <https://notis.nubic.northwestern.edu>. Please note that a username and password is required to use this program, and will be provided during site activation prior to training on the NOTIS system.

BEFORE a patient can be treated on study, please complete and submit the following items to confirm eligibility and receive an identification number:

- Patient's signed and dated informed consent form (upload to NOTIS and keep

- original hard copy in a secure location/study chart)
- Eligibility checklist (signed and dated by the treating physician – upload to NOTIS)
- Eligibility eCRF (complete in NOTIS)
- Copy of the pathology report (upload to NOTIS)

Training on eCRF completion will be provided at the time of site activation. Please refer to the eCRF demonstration videos on the CRO website for additional instructions on registering a patient.

The QAM will review the registration, register the patient, assign a subject identification number, and send a confirmation of registration to study personnel. Registration will then be complete and the patient may begin study treatment.

11.4 Data Submission

Once a subject is confirmed and registered to the study, eCRFs should be submitted according to the detailed data submission guidelines (provided in a separate document). Generally, all data are due within 10 days of each study visit.

11.5 Data Management and Monitoring/Auditing

This study will be conducted in compliance with the Data Safety Monitoring Plan (DSMP) of the Robert H. Lurie Comprehensive Cancer Center of Northwestern University (please refer to NOTIS for additional information). The level of risk attributed to this study requires high level monitoring, as outlined in the [DSMP](#). The assigned QAM, with oversight from the Data Monitoring Committee, will monitor this study in accordance with the study phase and risk level. Please refer to NOTIS for additional data submission instructions.

11.6 Adherence to the Protocol

Except for an emergency situation in which proper care for the protection, safety, and well-being of the study patient requires alternative treatment, the study shall be conducted exactly as described in the approved protocol.

11.6.1 Emergency Modifications

Investigators may implement a deviation from, or a change of, the protocol to eliminate an immediate hazard(s) to trial subjects without prior IRB approval.

For any such emergency modification implemented, an IRB modification form must be completed within 5 business days of making the change, and the QAM must be notified within 24 hours of such change.

11.6.2 Other Protocol Deviations

All other deviations from the protocol must be reported to the assigned QAM using the appropriate form.

A protocol deviation is any unplanned variance from an IRB approved protocol that:

- Is generally noted or recognized after it occurs.
- Has no substantive effect on the risks to research participants.
- Has no substantive effect on the scientific integrity of the research plan or the value of the data collected.
- Did not result from willful or knowing misconduct on the part of the investigator(s).

A protocol deviation may be considered an instance of Reportable New Information(RNI) if it:

- Has harmed or increased the risk of harm to one or more research participants.
- Has damaged the scientific integrity of the data collected for the study.
- Results from willful or knowing misconduct on the part of the investigator(s).

- Demonstrates serious or continuing noncompliance with federal regulations, State laws, or University policies.

11.7 Investigator Obligations

The Principal Investigator is responsible for the conduct of the clinical trial at the site in accordance with Title 21 of the Code of Federal Regulations and/or the Declaration of Helsinki. The PI is responsible for personally overseeing the treatment of all study patients. The PI must assure that all study site personnel, including sub-investigators and other study staff members, adhere to the study protocol and all FDA/GCP/NCI regulations and guidelines regarding clinical trials both during and after study completion.

The Principal Investigator at each institution or site will be responsible for assuring that all the required data will be collected, entered onto the appropriate eCRFs, and submitted within the study-specific timeframes. Periodically, monitoring visits may be conducted and the Principal Investigator will provide access to his/her original records to permit verification of proper entry of data. The study may also be subject to routine audits by the Clinical Trial Audit Committee (CTAC), as outlined in the DSMP.

APPENDIX A- CONTRACEPTION REQUIREMENTS

Investigators shall counsel FOCBP and male subjects who are sexually active with FOCBP on the importance of pregnancy prevention and the implications of an unexpected pregnancy. Investigators shall advise FOCBP and male subjects who are sexually active with FOCBP on the use of highly effective methods of contraception from the time of treatment initiation to 5 months (for FOCBP) or 7 months (for males with FOCBP partners) after the last dose of nivolumab. Highly effective methods of contraception have a failure rate of < 1% per year when used consistently and correctly.

At a minimum, subjects must agree to the use of two methods of contraception, with one method being highly effective and the other method being either highly effective or less effective as listed below:

HIGHLY EFFECTIVE METHODS OF CONTRACEPTION

- a) Male condoms with spermicide
- b) Hormonal methods of contraception including combined oral contraceptive pills, vaginal ring, injectables, implants, and intrauterine devices (IUDs) such as Mirena® by FOCBP subject or male subject's FOCBP partner. Female partners of male subjects participating in the study may use hormone based contraceptives as one of the acceptable methods of contraception since they will not be receiving study drug.
- c) Nonhormonal IUDs, such as ParaGard®
- d) Tubal ligation
- e) Vasectomy.
- f) Complete Abstinence*

*Complete abstinence is defined as complete avoidance of heterosexual intercourse and is an acceptable form of contraception for all study drugs. Subjects who choose complete abstinence are not required to use a second method of contraception, but female subjects must continue to have pregnancy tests. Acceptable alternate methods of highly effective contraception must be discussed in the event that the subject chooses to forego complete abstinence.

LESS EFFECTIVE METHODS OF CONTRACEPTION

- a) Diaphragm with spermicide
- b) Cervical cap with spermicide
- c) Vaginal sponge
- d) Male Condom without spermicide*
- e) Progestin only pills by FOCBP subject or male subject's FOCBP partner
- f) Female Condom*

*A male and female condom must not be used together

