Please note: This eligibility criteria is also applicable for patients enrolled for the preliminary expansion cohort to conduct preliminary efficacy analysis.

NOTE: Tissue or blood cell free DNA are allowed for genomic profiling of tumor. Profiling should have been performed at a CLIA certified lab ≤1 year prior to registration.

NOTE: Patients in the dose escalation phase are not required to have such mutations. Although genomic profiling is not required for dose escalation patients, it is encouraged in these patients prior to or after study registration if feasible.

3.1.7 Patients must be age ≥ 18 years; both male and females are eligible.

3.1.8 Patients must exhibit an ECOG performance status of ≤2.

3.1.9 Patients must have adequate organ and bone marrow function ≤ 14 days prior to registration, as defined below (Note: Blood transfusion or growth factors is not permitted within 14 days of registration):

absolute neutrophil count	≥ 1.5 x 10 ⁹ /L
hemoglobin	≥ 9 g/dL
platelets	≥ 100 x 10(9)/L
Total bilirubin	≤ 1.5 x ULN
Alanine amino transferase and aspartate aminotransferase	≤ 5 x ULN
Calculated creatinine clearance according to the Cockcroft and Gault equation	≥ 50 mL/min

3.1.10 Females of child-bearing potential (FOCBP) and men who are sexually active with FOCBP must agree to follow instructions for method(s) of contraception for the duration of treatment and the designated post-treatment period (5 months for females and 7 months for males; see Appendix A for details on appropriate contraception methods)

NOTE: A FOCBP is any woman (regardless of sexual orientation, having undergone a tubal ligation, or remaining celibate by choice) who meets the following criteria:

- Has not undergone a hysterectomy or bilateral oophorectomy
- Has had menses at any time in the preceding 12 consecutive months (and therefore has not been naturally postmenopausal for > 12 months)

3.1.11 FOCBP must have a negative pregnancy test ≤ 7 days prior to registration.

3.1.12 Patients must be able to swallow oral medication.

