- In the absence of clear alternative etiology, all events of an inflammatory nature should be considered to be immune-related
- Topical or inhaled steroid therapy should be considered for low-grade events
- Systemic corticosteroids should be considered for a persistent low-grade event or for a severe event
- More potent immunosuppressives (i.e. infliximab, mycophenolate mofetil, etc.) should be considered for events not responding to systemic steroids

If the investigator has any question in regards to an AE being an irAE, the investigator should immediately contact the principal investigator. Treatment modifications will not be required for AEs that are clearly not attributed to investigational drugs (such as an accident) or for laboratory abnormalities that are not deemed to be clinically significant.

Nausea and vomiting have been commonly observed in clinical trials with veliparib. Gastrointestinal toxicities, predominantly nausea and vomiting, were observed with veliparib as single-agent therapy and most frequently reported at higher doses (300 – 400 mg BID). Of the subjects treated with single agent veliparib at 300 – 400 mg BID dose levels, 15% required dose reduction, 5% delayed or interrupted dosing and 2% discontinued due to nausea. To optimize dose intensity and maintain subject quality of life, early initiation or prophylactic management with scheduled anti-emetic therapy (5HT-3 antagonists, metoclopramide, prochlorperazine) and/or lorazepam should be considered. In addition, it has also been observed that tolerance to these toxicities may develop over time. Management should include counseling regarding these toxicities and may include interruption of dosing, dose modification or veliparib discontinuation.

Treatment modifications may be required in the event of treatment-related toxicity. General guidelines regarding treatment modification are provided in Table 4.5 and 4.6. **Dose modifications should be implemented only if toxicities are attributed to respective drugs (nivolumab or veliparib). If there is uncertainty or overlapping toxicities, both drugs should be held and or dose modified according to the guidelines.**

All toxicities will be graded according to NCI CTCAE V4.03 (Appendix B).

Should a female patient become pregnant or suspect she is pregnant while participating in this study, she should inform her treating physician immediately. Similarly if a male patient impregnates a female, the treating physician should be informed.

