5.0 STUDY PROCEDURES

Table 5: Study timeline

	Screening ^{a,b,c}	Induction (7 days) ^c	Cycle 1 (Cycle=28 days)			Cycle 2-4		Cycle 5 +	End of Treatment ^o	Follow Up ^p
		D1	D1	D8	D15	D1	D15	D1		
Study window				±1 day	±1 day	±3 days	±3 days	±3 days	±7 days	q3months
Informed Consent	X									
Medical History	X		X	X		X		X	X	
Physical Exam	X	X	X	X	X	X	X	X	X	
Vitals signs ^{d,i}	X	X	X	X	X	X	X	X	X	
ECOG PS	X	X	X	X			X	X	X	
AE reporting ^q		X	X	X	X	X	X	X	X ^q	X ^q
Concomitant Medications		X	X	X	X	X	X			X
CMP ^e	X	X	X	X	X	X	X	X	X	
CBC with differential ^f	X	X	X	X	X	X	X	X	X	
Pregnancy test ^g	X ^g		X							
Thyroid function test ^h	X									
PT/INR	X ⁱ									
Imaging (CT or MRI) ^j	X					X ⁱ		X ^j	X	
Tumor biopsy ^k	X									
Mutation testing	X ^r									
Blood for Tumor Markers ^l		X	X			X ^l			X	
Nivolumab infusion ^m			X		X	X	X	X ^m		
Veliparib ⁿ		X	X			X		X		
Survival										X

- Informed consent must be signed ≤ 30 days before registration. If signature is outside that window the patient must sign a new consent.
- Pre-study H&P and all labs must be ≤ 14 days before registration. Tumor measurements and radiologic evaluations must be ≤28 days before registration.
- The maximum time interval between registration and the first dose of study drug will be 14 days.
- Vital signs include pulse and blood pressure. Weight will be recorded at baseline. Height will be recorded at baseline only.
- Serum Chemistry will include calcium, chloride, magnesium, phosphorus, creatinine, sodium, potassium, blood urea nitrogen, bicarbonate, glucose, total bilirubin, aspartate aminotransferase (AST), alanine aminotransferase (ALT), alkaline phosphatase, albumin, and total protein.

- f. CBC: Performed pre-dose at each treatment visit (Day 1 & 15 of Cycles 1-4, and Day 1 of Cycle 5+). For patients experiencing significant drop in WBCs or platelets felt related to treatment, CBCs should be obtained more frequently (weekly or more frequently) to assess timing for retreatment or need for transfusion support.
- g. Serum or urine test only for women of childbearing potential; must be tested within 7 days prior to registration as well as C1D1 (within 24 hours prior to nivolumab treatment).
- h. Thyroid function tests will include thyroid stimulating hormone (TSH) with reflexfree T4. This will be done at baseline then only as clinically indicated thereafter.
- i. PT/INR is required at baseline (≤ 28 days prior to registration) for patients on anticoagulants.

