- j. Imaging (either CT scan or MRI and PET if applicable) will be performed at screening, ≤ 28 days prior to registration. The same modality used at baseline should be used throughout for imaging. CT imaging will include chest, abdomen, and pelvis. Neck will be included only if measurable lesions are present. Scans will then take place every 2 cycles (8 weeks) starting with Cycle 3 Day 1 (- 7 days). Tumor measurements will be performed using RECIST 1.1 or Lugano classification. Progressive Disease (PD) must be confirmed by repeat scan within 8 weeks.
- k. Patients will undergo a fresh tissue biopsy prior to study enrollment, unless deemed to be clinically inappropriate per PI. If a fresh biopsy is not feasible, an archival tissue sample should be obtained (a cell block is preferred, however 15 unstained slides will suffice). Tissue should be obtained by any means possible, but patients will not be excluded from the study if tissue is not available. The samples will be obtained for correlative studies – see section 9.0 and separate lab manual for details.
- l. Study labs will be collected for tumor markers pre-dose on Induction Day 1, C1D1, C3D1, and at the End of Treatment visit. See section 9.0 and separate lab manual for more details.
- m. Nivolumab will be administered as follows:
 - Cycles 1-4: given at a fixed dose of 240mg IV over 30 minutes (-5 / +15 minutes) every 2 weeks
 - Starting with Cycle 5 Day 1: 480mg IV over 30 minutes (-10 / +15 minutes) every 4 weeks until disease progression, intolerability, or withdrawal of consent.
 - Vital signs will be monitored prior to, throughout, and after the nivolumab infusion according to Table 4.2.
- n. Veliparib will be taken orally at the assigned dose twice a day until disease progression, intolerability, or withdrawal of consent. It will be initiated as monotherapy during a 7-day induction period. Starting with Cycle 1 Day 1, veliparib will be given twice daily in combination with scheduled nivolumab infusions. Veliparib may be taken with or without food. Patients will be given a drug diary to maintain for compliance. Veliparib dosing may take place independently of nivolumab. On the day of a study visit, lab values should be checked against sections 4.4 and 4.5 for continued dosing.
- o. The end of treatment visit should occur 30 days after the last dose of study treatment (± 7 days) or before starting another line of treatment, whichever comes first.

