7.2.6 Other events requiring immediate reporting Overdose

An overdose is defined as a patient receiving a dose of investigational product in excess of dose detailed in this protocol.

Any overdose of a study patient with the investigational product, with or without associated AEs/SAEs, is required to be reported within 24 hours of knowledge of the event. If the overdose results in an AE, the AE must also be recorded on the AE eCRF. Overdose does not automatically make an AE serious, but if the consequences of the overdose are serious, for example death or hospitalization, the event is serious and must be reported as an SAE. The investigator will use clinical judgment to treat any overdose.

Pregnancy

Pregnancy in a female patient who has received investigational product is required to be reported within 24 hours of knowledge of the event.

Patients who become pregnant during the study period must not receive additional doses of investigational product but will not be withdrawn from the study. The pregnancy will be followed for outcome of the mother and child (including any premature terminations).

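### Appendix A requires pregnancy testing to continue in women who choose abstinence, but Table 5 schedules none after Cycle 1 Day 1 although dosing is open-ended

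*Combined protocol and SAP*

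**What the plan says.** Appendix A asks subjects to use two contraceptive methods, at least one of them highly effective, from the start of treatment until 5 months after the last nivolumab dose for females of child-bearing potential (FOCBP). Complete abstinence removes the need for a second method, on the condition that "female subjects must continue to have pregnancy tests". No frequency is given.

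The schedule of tests is in section 5.0. The pregnancy-test row of Table 5 is marked at Screening and at Cycle 1 Day 1 and nowhere else. Footnote g says the same in prose: FOCBP "must be tested within 7 days prior to registration as well as C1D1 (within 24 hours prior to nivolumab treatment". Section 3.1.11 covers only the screening test: "FOCBP must have a negative pregnancy test ≤ 7 days prior to registration".

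Dosing has no fixed maximum. Footnote n of Table 5 states: "Veliparib will be taken orally at the assigned dose twice a day until disease progression, intolerability, or withdrawal of consent". Table 4.1 has nivolumab continuing on the same terms. On pregnancy during the study, section 7.2.6 states: "Patients who become pregnant during the study period must not receive additional doses of investigational product", and it requires a report within 24 hours. Section 4.4 relies on the patient to raise the alarm: "Should a female patient become pregnant or suspect she is pregnant while participating in this study, she should inform her treating physician immediately".

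**The concern.** A mandatory instruction to continue testing has no schedule behind it. A site that follows Table 5 exactly stops testing on the first day of combination treatment, while exposure continues indefinitely. The stop-dosing rule works only if a pregnancy is noticed, and Table 4.5 lists embryo-fetal toxicity under veliparib. After Cycle 1 Day 1, detection depends on the patient's own report, routine history and physical examination, or a test the investigator chooses to order. These are less sensitive to early pregnancy than a scheduled test, and twice-daily veliparib and nivolumab can continue in the meantime. Because Table 5 does not require a later test, omitting one is not a deviation from the schedule, and practice may differ between clinicians.

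What is at stake is participant safety and the consistency of the protocol. No efficacy or dose-finding analysis depends on it.

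**Working it through.** The plan gives no figure to reproduce, so the check is a comparison of the text followed by a simple count.

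**Text comparison**

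| Place | What it provides |
|---|---|
| Appendix A | Testing must continue for abstinent women; no interval |
| Section 3.1.10 | A woman "remaining celibate by choice" still counts as FOCBP |
| Section 3.1.11 | One test, within 7 days before registration |
| Table 5, pregnancy row | Screening and C1D1; blank at C1D8, C1D15, Cycles 2-4, Cycle 5+, End of Treatment and Follow Up |
| Table 5, footnote g | The same two time points, in prose |
| Table 5, footnote h | Thyroid tests repeated when clinically indicated; footnote g has no such clause |
| Section 7.2.6 | No further dosing in pregnancy |

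Because footnote g repeats the two time points in words, the blank cells are not an artefact of how the table was read. Veliparib starts as a 7-day induction before C1D1, so of the two scheduled tests one (C1D1) falls after the first veliparib dose and none falls later.

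**Length of the untested period**

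Inputs: 28-day cycles, the 7-day induction, and the 24-week endpoint in section 2.2.5.

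- Week 24 counted from the first veliparib dose: 24 × 7 − 7 = 161 days (23 weeks) after C1D1.
- Week 24 counted from C1D1: 24 × 7 = 168 days.

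**Effect of testing on Day 1 of each cycle from Cycle 2**

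Day 1 of Cycles 2 to 7 falls 28, 56, 84, 112, 140 and 168 days after C1D1.

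- By day 161: 5 tests, or 5 + 1 = 6 with End of Treatment.
- By day 168: 6 tests, or 6 + 1 = 7 with End of Treatment.
- Planned gap: 28 days. With the ±3-day windows at both ends, the gap between later cycles is 28 − 6 = 22 to 28 + 6 = 34 days.

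**Total burden**

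The number of FOCBP among the 6 expansion patients is not stated. Assuming 0 to 6, the added tests number from 0 to 6 × 7 = 42 for treatment to week 24. The 42 is an upper limit, because it counts both a Cycle 7 Day 1 test on day 168 and an End of Treatment test for every woman.

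**Rough bound on expected pregnancies**

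Appendix A describes highly effective methods as failing in under 1% per year with consistent, correct use. If all 6 patients were FOCBP treated for 168 days, exposure would be 6 × 168/365 = 2.76 person-years, and the expected number under 2.76 × 0.01 ≈ 0.028. Imperfect use would raise this; a second method or fewer FOCBP would lower it.

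**The case against.** The strongest reply is that nothing conflicts. The Appendix A sentence qualifies an exemption: abstinence waives the second method but not the study's tests. Section 3.1.10 supports this by keeping celibate women within FOCBP. On that reading the C1D1 test, coming after screening, satisfies the sentence, and no section promises testing every cycle. This reading is plausible. It removes the contradiction but not the gap, since one test after veliparib starts is little to continue over open-ended dosing.

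Other safeguards also exist: contraception with counselling, a duty to report a suspected pregnancy, medical history on Day 1 of every cycle, and a physical examination at every treatment visit. These are real, and they mean self-report is not the only route to detection, though none replaces a test in early pregnancy. The expected yield in six patients is very small, and the women Appendix A addresses here have the lowest risk. Both points stand and bear on priority. However, every FOCBP follows the same Table 5 row, including women relying on methods that can fail.

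Finally, the per-cycle interval is not in the documents, and testing that ends at End of Treatment does not cover the 5-month contraception period. Both are correct. The interval is a judgement based on the visit schedule. After End of Treatment dosing has stopped, so the stop-dosing rule is no longer at issue, and follow-up may be by telephone.

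**Conclusion.** The concern holds. The protocol schedules no pregnancy test after C1D1, while dosing is open-ended and must stop in pregnancy. Whether Appendix A contradicts Table 5 or is merely unclear depends on how its sentence is read, but the practical result is the same: 161 to 168 days of combination dosing to week 24 without a scheduled test, and longer for anyone who stays on treatment.

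The day counts assume treatment without interruption to week 24 on 28-day cycles. The 0 to 42 added tests assume 0 to 6 FOCBP in the expansion cohort. This is a cheap safety correction that should be made. Its small expected yield in this cohort lowers its urgency. The MTD and objective response rate are not affected.

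**What to change.** In Table 5 and footnote g, add a urine or serum pregnancy test for FOCBP on Day 1 of each cycle from Cycle 2, before that day's nivolumab dose, and at the End of Treatment visit. In Appendix A, tie the testing condition for abstinent women to that schedule. Deleting the condition, or only pointing it to the present Table 5, would tidy the wording but leave the untested period unchanged.

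The cost is one row edit, one footnote edit and one cross-reference, plus 6 or 7 low-cost tests per FOCBP treated to week 24. Footnote f already has the blood count "Performed pre-dose at each treatment visit (Day 1 & 15 of Cycles 1-4, and Day 1 of Cycle 5" onward, and Table 5 marks both blood count and chemistry at these visits and at End of Treatment. No visit is added and no analysis changes.
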